4.2 Challenge of Cardiovascular MRI in Children

The clinical value of MR is well established for a variety of cardiovascular disorders (5–9). Children with congenital heart disease (CHD) typically have both intra-cardiac and extra-cardiac vascular anomalies. Therefore, the ability to visualize both types of morphologic abnormalities is crucial. Although echocardiography is readily available, it may leave several morphologic and hemodynamic questions unresolved due to issues such as inadequate acoustic window. Cardiac CT with either single or dual source technology can yield high spatial resolution images with increasingly small radiation doses. However, sub-milliSievert doses are achievable only in the most ideal situations (low body mass index, sinus rhythm with excellent beta blockade). Exposure to radiation, however low the dose, should be considered only when alternative methods are not available. Furthermore, neonates and infants may have heart rates that challenge the temporal resolution of even dual source CT scanners. With MRI, the temporal resolution of cine imaging can be adjusted to cope with even the fastest heart rates (10). MRI has been shown to be a versatile, non-invasive, and non-radiating technique for the evaluation of neonates, infants, and children, including those who are critically ill (9,11,12).

In young children, the small caliber of the heart and blood vessels requires higher spatial resolution than in adults (5,7) for comparable detail. For adults and larger children, spatial resolution as previously reported (13–15) may be entirely adequate; for small children with diminutive central vessels, the requirements for high spatial resolution are much more stringent. Further, children (particularly newborns to age 6) also often require the MRI exam to be done under general anesthesia (9) as they are unable to obey commands and may be critically-ill.

4.3 MRI clinical standard of care in children with CHD

In children with CHD, echocardiography is universally regarded as the primary diagnostic imaging modality. When echocardiography is inconclusive, MRI is the preferred second line imaging modality due to the absence of ionizing radiation and the ability to incorporate functional as well as anatomic information. MRI for pediatric CHD routinely involves the use of GBCAs to evaluate extra-cardiac vascular anatomy, which may be complex and anomalous, but knowledge of which is essential to inform patient management. Gd is a rare earth metal not found naturally in biological systems, but with paramagnetic properties that greatly enhance the MRI signal. Because free Gd ions are toxic, GBCAs are stable chelates wherein the Gd ions are tightly bound with very high association constants. The chelating molecule in turn modulates the biological distribution,

potency and pharmacokinetics of the contrast agent. Most GBCAs are small diffusible molecules that, following bolus intravenous injection, sustain a short intravascular peak and quickly access the interstitial space. Therefore, these extracellular GBCAs are useful mainly for first-pass MR angiography, wherein the images are acquired during the initial 15-30 seconds post-injection before the GBCA leaks from the intravascular space. In children with CHD, this limited time window will generally preclude simultaneous high-resolution cardiac and vascular image acquisition, due to the requirement for gating to freeze cardiac motion. However, high resolution imaging of the intracardiac structures, including the great arteries, the cardiac chambers, the valves, and the coronary arteries and the outflow tracts, is essential for planning surgery or other interventions for these patients.

Ablavar (Ablavar®, Lantheus Medical) is a GBCA, which binds reversibly to plasma proteins and therefore has a longer intravascular residence time and higher potency (r_1 relaxivity) than the purely extracellular gadolinium agents. At any time, 70% - 80% of the Ablavar in the blood is reversibly bound to serum albumin and the remainder is distributed in the extracellular space. The binding to plasma proteins slows the initial distribution of Ablavar from the blood pool to the extracellular fluid space such that, whereas for the purely extracellular GBCAs the distribution half life is < 5 minutes, for Ablavar the distribution half life is on the order of 25 minutes. Because of its longer intravascular residence time, Ablavar extends the useful time window for vascular imaging to 20-30 minutes beyond the first pass. Once the distribution phase is complete, Ablavar and the other GBCAs are diluted by the extracellular fluid space (~15 liters in an average adult or ~30% of body weight in a child under 6 years) and their effectiveness in enhancing the vascular signal is correspondingly diminished. Therefore, from the perspective of vascular MRI, the duration of the initial distribution phase is the most relevant because the strength of the vascular signal is determined by the concentration of the agent in the blood when the scan is being performed. Once distributed, the elimination half-life (due to renal excretion) of Ablavar is on the order of 19 hours.

Ablavar is approved as a contrast agent for MR angiography in adult patients with peripheral vascular disease and has become the agent of choice at many institutions for pediatric CHD. Compared to the purely extracellular GBCAs, Ablavar has higher potency per unit dose of Gd (r_1 relaxivity), provides a longer time window for vascular imaging and leaks into the interstitial fluid space more slowly. However, like the extracellular GBCAs, its primary mode of elimination is by renal filtration of the unbound plasma fraction. Although this is an improvement over the purely extracellular agents, an even longer vascular residence time would be desirable in children for several reasons. Firstly, for combined and simultaneous high-resolution cardiac and vascular imaging in CHD patients, the concentration of contrast agent in the blood should remain constant over the several minutes of the imaging scan. Secondly, in patients under anesthesia or sedation it is sometimes necessary to interrupt or repeat a scan if the anesthesiologist needs to adjust the depth or type of sedation on a patient specific basis. Inadequate sedation may result in patient motion artifact which can render the study non-diagnostic. Time spent adjusting the sedation parameters and confirming physiologic stability may push the image acquisition window beyond the optimum time window for Ablavar, resulting in diminished image quality even if motion artifact is absent.

Therefore, the overall effect of Ablavar® is qualitatively similar to the GBCAs with similar limitations, but on an expanded time scale which may be adequate if the study goes smoothly but which may result in compromised image quality if scans need to be paused or repeated. The hypothesized advantages of Feraheme over Ablavar are the purer and much longer intravascular residence time (intravascular half life of 15 hours vs 0.5 hours), such that high-resolution steady-state cardiac and vascular imaging can be completed successfully, whether or not scans need to be paused or repeated.

4.4 Safety Concerns with GBCAs

GBCAs have been used for over a quarter of a century and have a highly favorable safety profile, which is predominantly based on their stability *in vivo*. GBCAs are chelates designed to tightly bind gadolinium ions because free gadolinium ions are toxic (16). In recent years, some safety concerns have been raised relating to the association of nephrogenic systemic fibrosis (NSF) with GBCA exposure for patients with renal impairment, and observation of gadolinium deposition in brain tissue, even in patients with normal renal function (17–22). The gadolinium deposition in tissue may be particularly worrying in children because of their projected life-expectancy and in whom Gd may potentially persist indefinitely. Furthermore, there are concerns of hypersensitivity to GBCA injections (23,24) and association of Ablavar with prolongation of the QT interval on the ECG, which may pose more concern for cardiac arrhythmias in children with CHD than those with normal hearts.

[Nephrogenic systemic fibrosis (NSF)] In 2006, associations between NSF and GBCA exposure (25,26) led to a boxed warning alert by the US FDA (27) and the EMA (28) to restrict the use of GBCAs in patients with renal insufficiency. Autopsy studies have reported the presence of gadolinium in skin, heart, blood vessels, lungs, lymph nodes, spleen, liver, kidney, and dura of patients with NSF (16). Almost a decade later however, the pathophysiology of NSF remains unclear. Nevertheless, a consistent body of literature does suggest that slow clearance of GBCAs in patients with impaired renal function predisposes to transmetalation with release of free gadolinium ions, which have fibrogenic effects (29). The diagnosis of NSF is complex (30) and should only be made when clinical and histopathological criteria set forth by the Yale NSF Registry are met (31). NSF is described as skin discoloration and swelling progressing to erythematous papules, brawny lesions, and subcutaneous sclerosis (32,33) and occurs within 2-3 months of exposure to GBCAs, but late onset cases have been reported (34). Recently, a new entity, termed gadolinium-associated plaques, was reported in two patients by Gathings et al. (35), whereby neither patient had NSF while only one patient had renal failure. Both patients, however, had erythematous plaques associated with sclerotic bodies thought to be pathognomonic for NSF. This occurrence was related to gadodiamide.

The risk of GBCA-associated NSF is highest in those with an estimated glomerular filtration rate (eGFR) < 30mL/min/1.73m² (1-7%) and those with acute renal failure (12-20%). The risk is lower for those with moderately decreased renal function (30-59mL/min/1.73m²) and even less for those with mild renal impairment (60-89mL/min/1.73m²). While there are a multitude of publications on GBCA-associated NSF, the most interesting reports are cases in which NSF did not develop in those with severe chronic kidney disease (CKD) (15-29 mL/min/1.73m² eGFR), who were exposed to high doses of GBCAs (36,37). It is thought that other confounding risk factors beyond

impaired renal function such as concomitant acidosis, infection, acute pro-inflammatory events, immunosuppression, high-dose erythropoietin therapy, elevated iron /calcium /phosphate levels, and vasculopathy may play a role in the initiation of the NSF disease cascade.

Zou et al. (33) in their review of 370 biopsy confirmed cases of NSF, suggest that eliminating risk factors may substantially reduce the risk of NSF without having to shift to other imaging modalities, which may incur risk of radiation and iodinated contrast-induced nephropathy. These preventable risk factors include using the lowest dose possible for diagnostic result (limiting GBCA dosage to $<0.1\text{mmol/kg}$), avoiding non-ionic linear GBCAs in those on dialysis or having $\text{eGFR} < 30\text{mL/min/1.73m}^2$, dialyzing dialysis-dependent patients promptly after exposure, and delaying GBCA administration in the setting of acute renal failure particularly when proinflammatory conditions may exacerbate oxidative stress. The Contrast Media Safety Committee of the ESUR (29) also recently published recommendations for NSF-risk mitigation where they outlined the level of evidence and identified classes of recommendations for clinical practice. For the pediatric population, no specific evidence based-guidelines exist. Guidelines for adults are typically used. There have been 10 biopsy-proven pediatric cases of NSF, but since the implementation of guidelines, no new cases in children have been reported (38). To date, no cases of NSF have been reported in very young children (38). However, it is known that children younger than 2 years have immature renal function (39). The glomerular filtration rate (GFR) of pre-term and term newborns can be as low as 40 ml/min/1.73m^2 , and it gradually increases to 66 ml/min/1.73m^2 at 2 weeks after birth (39). Due to concerns about nephrogenic systemic fibrosis (NSF), The European Society of Urogenital Radiology warns against the use of GBCA, including gadofosveset, in children less than 1 year old (40). **Therefore, a significant portion of the children in our study will have immature renal function with an unknown, but likely very low risk of developing NSF.**

[Possible retention in brain and other tissues] In July 2015, the US FDA issued a safety announcement regarding deposits of GBCAs in the globus pallidus and dentate nuclei of patients who have undergone multiple GBCA-enhanced MRI (41). The announcement was in response to reports of residual gadolinium deposits on non-contrast MRI of patients who had undergone multiple GBCA-enhanced MRI exams (42) -- some of whom had normal renal function (19,20), and in those exposed to ionic linear GBCA (gadopentetate dimeglumine) rather than macrocyclic GBCA (gadoteridol) (21). In a pictorial essay, Caruso et al. (17) first alluded to this phenomenon in 2001, but it was not until recently that the findings were publicized by Kanda et al. (18,20,21), confirmed by Errante et al. (19), and expanded by McDonald et al. (22). Their work is limited to patients with intracranial T1 shortening whereas work by others (43–45) suggests that insoluble gadolinium (in the form of gadolinium phosphate in bone tissue) may make up another portion of residual gadolinium deposit in the body. However, it remains unknown whether these deposits have any adverse clinical implications. Their findings need confirmatory work, particularly to better understand whether certain types of GBCAs are more prone to residual deposition. **If future research points to significant toxicity of these gadolinium deposits, young children exposed to GBCA, including the pediatric CHD population in the Ablavar group of our study, may be subject to higher risk due to their longer life expectancy compared to adults.**

[Hypersensitivity] Although the rate of reported cases of NSF has declined, issues relating to

hypersensitivity remain. The overall rate of AEs for all GBCAs given at clinical doses (0.1-0.2mmol/kg) is estimated to be between 0.07 to 2.4% (46). As a comparison, the rate of AEs for low-osmolality iodinated contrast agents is 0.15% (47) to 0.2% (46). While hypersensitivity-like reactions associated with GBCAs vary from 0.004% to 0.7%, the frequency of serious life-threatening anaphylactic reactions associated with these agents is exceedingly uncommon (0.001 to 0.01% (46) vs. 0.04% for nonionic low-osmolality iodinated contrast (46)). According to analysis of data reported in FDA MedWatch by Prince et al. (24), the risk of death associated with GBCA administration is less than 1 in a million ('equivalent to the risk of dying from a chest X-ray, consuming 0.5L of wine, smoking 1.4 cigarettes, or traveling 86 miles by car'). In contrast, the fatality rate for iodinated contrast is 0.9 per 100,000 injections or 2.1 fatalities per one million studies using low-osmolality contrast agents based on FDA data from 1990-1994 (46). The death rate for ionic linear GBCAs is seven times higher than from nonionic linear agents (24) whereas the frequency of acute adverse reactions to GBCAs is eight times higher in those with prior reactions to GBCAs. For those with prior reactions to GBCAs, the administration of gadobenate dimeglumine is contraindicated (46). Other risk factors for acute hypersensitivity reactions include a history of asthma and multiple drug or food allergies. Although there is no cross-reactivity between GBCA and iodinated contrast agents, the frequency of GBCA-related adverse event is 2.3-3.7 times higher in those with prior reaction to iodinated contrast (48).

4.5 What is Feraheme and what is its potential as an alternative MRI contrast agent?

Feraheme® (AMAG Pharmaceuticals, MA) is a proprietary formulation of the iron supplement ferumoxytol. Initially designed as an intravascular MRI contrast agent, Feraheme® was approved as a bolus intravenous (IV) iron supplement by the FDA in 2009, specifically for the treatment of iron deficiency anemia (IDA) secondary to chronic kidney disease (CKD). Each manufacturer-provided 17-mL vial contains 510mg elemental iron (30 mg Fe /mL) and was administered as an IV bolus in as little as 17 seconds (1 mL/sec), a practice recently revised in favor of slow infusion over 15 minutes (49). The therapeutic dose for the treatment of IDA calls for two 510-mg injections given 3-8 days apart. Compared to other IV iron supplements, Feraheme was developed to have lower free iron release (50), decreased immunologic allergic reaction, and improved safety profile (50-52). As an ultra-small superparamagnetic iron oxide (USPIO) nanoparticle, Feraheme has a long intravascular half-life of 14 hours, high r_1 relaxivity, and is incorporated into the hematopoietic pathway as supplemental iron once the outer carbohydrate shell is degraded (53). These properties along with its approved therapeutic use in patients with kidney dysfunction and lack of gadolinium make Feraheme an attractive alternative to GBCAs for first-pass and steady state MRI (53,54). To date, imagers have explored Feraheme for cardiovascular applications (55-57), renal transplant imaging (58), inflammation imaging (59-61), and cancer imaging (62-65).

By exploiting the imaging properties of Feraheme® appropriately in small children, it is possible to acquire images with unprecedented detail, without the need for breath holding. Our group recently developed a technique termed 4-dimensional MUSIC-MRI, which produces 4 dimensional contrast-enhanced images of the beating heart in children, without breath holding (1). Additionally, Feraheme® can overcome issues related to both short-term and long-term gadolinium deposition in soft tissues. In our practice at UCLA, Feraheme®-enhanced MRI has informed clinical decision-making in children with complex and life threatening diseases in ways that would otherwise not have been possible. For this reason, we feel that we have sufficient

preliminary data to support the prospect of direct benefit (PDB) to patients who undergo MRI with Feraheme® in our investigator-initiated, single center, exploratory, open label clinical trial.

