	
Exclusion Criteria:
 
 1. Standard clinical contraindications to MRI, including subjects with cochlear implants and implanted cardiac devices 2. Subjects with past or current diagnosis of iron overload due to hereditary hemochromatosis or other causes (for subjects receiving Feraheme injection only). 3. Subjects with known hypersensitivity or allergy to iron oxide particles. 4. Subjects with renal insufficiency defined as estimated glomerular filtration rate (eGFR) $< 40 \text{ mL/min/1.73m}^2$ (for subjects receiving Ablavar injection only). 5. Subjects who are critically ill at the time of MRI and for whom the period of general anesthesia and separation from the critical care nursery or intensive care unit poses added risk as deemed by referring cardiologists, cardiac surgeons or the managing radiologist (for Part II only). 6. Other medical conditions, in the judgment of the clinician investigator, that would increase the risks to the child related to participation in the study.
TEST PRODUCT, DOSE, AND ROUTE OF ADMINISTRATION	Ferumoxytol (Feraheme®): Stock Feraheme® formulation will be diluted by a factor of ≤ 30 with normal saline and administered by slow intravenous infusion for a total dose of 4 mg of iron per kg of body weight. The total infusion time will be 10 minutes.
CONTROL PRODUCT, DOSE AND ROUTE OF ADMINISTRATION	Gadofosveset (Ablavar®): Manufacturer recommended dosing of 0.03mmol/kg (0.12mL/kg) will be diluted 4-8x (based on body size) with normal saline and administered intravenously over 15 seconds at a rate of 0.3-1 mL/sec, depending on patient size.
STUDY DURATION	Screening and imaging: 1 day Total duration of the study: 5 years.
CONCOMITANT MEDICATIONS	Allowed: The subjects are allowed to take concomitant medications as necessary or directed by the patient's physician. Prohibited: None.
EFFICACY EVALUATIONS	In Part I, the Feraheme®-enhanced ventilator-gated MUSIC-MRI image quality will be scored and compared with Ablavar®-enhanced ventilator-gated MUSIC-MRI. In Part II, the ventilator-gated MUSIC-MRI image quality will be scored

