	
3. The patient's legal guardian(s) decide(s) to participate in one of the study groups.4. Patient undergoes general anesthesia per our institutional standard protocol or is transferred from the neonatal ICU already sedated and intubated.5. Patient undergoes cardiovascular MRI (ventilator-gated MUSIC-MRI) using either Feraheme or Ablavar and with continuous monitoring of vital signs and any AEs. AE treatments are delivered as needed.6. Patient recovers from anesthesia or sedation.7. Patient is followed up at 60 days post-MRI via a medical record review to capture any additional AE.
	
Part II:
 
1. Patient is referred for cardiovascular MRI.2. The Investigators discuss with the patient's legal guardian(s) the study design and risks/benefits for either Feraheme or Ablavar administration, depending on the outcome of Part I.3. The patient's guardian(s) provide written informed consent form.4. Patient undergoes general anesthesia per our institutional standard protocol or is transferred from the neonatal ICU already sedated and intubated.5. Patient undergoes cardiovascular MRI (ventilator-gated MUSIC-MRI and self-gated MUSIC-MRI) using the contrast agent determined in Part I and with continuous monitoring of vital signs. AEs are recognized immediately and treatment delivered as appropriate.6. Patient recovers from anesthesia or sedation.7. Patient is followed up at 60 days post-MRI via a medical record review to capture any additional AE.

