9 SUBJECT SELECTION

9.1 Study Population

Pediatric patients of all ethnicities, age newborn to 6 years, of either gender with known or suspected CHD will be recruited. This specific age population has been chosen because our preliminary experiences suggest that the PDB is greatest in the smallest and sickest children. Furthermore, all patients of ages < 6 years undergoing cardiac MR imaging are routinely examined under anesthesia with controlled ventilation independently of our study and under the direct and

continuous observation of a pediatric anesthesiologist or neonatologist. These elements minimize the relative risk of Feraheme® administration by enabling airway protection and the ability to perform non-breath-held diagnostic studies in potentially fragile patients. Our study population will include patients with any types of CHD who are clinically referred to cardiovascular MRI; however, we expect our patient recruitment to be concentrated in more complex forms of CHD, such as Tetralogy of Fallot, because these are the patients that typically have inadequate echocardiographic exams and are referred for MRI. We do not expect our study population to have eGFR<40 mL/min/1.73m², although renal insufficiency is an exclusion criteria for the Ablavar® group of Part I study.

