9.3 Exclusion Criteria

1. Standard clinical contraindication to MRI, including subjects with cochlear implants and implanted cardiac devices
2. Subjects with past or current diagnosis of iron overload due to hereditary hemochromatosis or other causes (for subjects receiving Feraheme® injection only).
3. Subjects with known hypersensitivity or allergy to iron oxide particles.
4. Subjects with renal insufficiency defined as estimated glomerular filtration rate (eGFR) < 40 mL/min/1.73m² (for subjects receiving Ablavar® injection only).
5. Subjects who are critically ill at the time of MRI and for whom the period of general anesthesia and separation from the critical care nursery or intensive care unit poses added risk as deemed by referring cardiologists, cardiac surgeons or the managing radiologist (for Part II only).
6. Other medical conditions, in the judgment of the clinician investigator, that would increase the risks to the child related to participation in the study.

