11.1.1 Justification for Parents Participation in Patient Group Assignment

We plan to allow parents to participate in the decision about treatment assignment in Part I of this open-label, evaluator-blinded study. Feraheme-based imaging is in use at several pediatric specialty centers, including UCLA whereby Feraheme is used more frequently than GBCA-based imaging for children in our study age-group. In the current state of professional equipoise, we judge it appropriate to allow parents to participate in the choice of agent. There is no *a priori* reason to expect MRI image quality, ventricular or aortic wall definition, or the risks of anaphylaxis or other important AEs to be influenced by parental preferences; thus the generalizability of our scientific conclusions will not be diminished by allowing parents to influence the treatment assignment for their children. Recruitment of children in clinical studies is a challenging process. Based on our clinical investigative experience in the particular patient population at UCLA, many parents and/or legal guardians are more willing to participate in a study without randomization of treatment than one that required randomization of the child's treatment. We expect this route of recruitment will facilitate recruitment and successful completion of the study. In scenarios where the patient's legal guardians defer and ask the managing clinician to make 'the best choice', the decision will be based on the apparent needs of the trial at the time and the patient will be assigned the group that is under-enrolled with reference to the target enrollment. If our patient group assignment method results in a severely distorted imbalance (e.g. nearly all parents elect either Feraheme or Ablavar), the DMC will be convened and asked to advise on a corrective measure, which may include changing the patient group allocation method.

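### Exclusion 4 bars Ablavar for eGFR below 40 but not for acute renal failure, which section 4.4 names as a separate highest-risk group for NSF

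*Combined protocol and SAP*

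**What the plan says.** Section 4.4 sets out the NSF risk by renal status. Risk is highest with eGFR below 30 mL/min/1.73m² (1-7%) "and those with acute renal failure (12-20"%), and lower at 30-59. The same section reports a review of 370 biopsy-confirmed cases whose preventive measures include putting off gadolinium in acute renal failure.

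The renal criterion for Ablavar is item 4 of section 9.3, repeated in the synopsis: "Subjects with renal insufficiency defined as estimated glomerular filtration rate (eGFR) < 40" mL/min/1.73m², for Ablavar recipients only. Acute renal failure appears in no inclusion or exclusion criterion.

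Item 5 removes critically ill children for whom anesthesia and separation from intensive care add risk, "as deemed by referring cardiologists, cardiac surgeons or the managing radiologist (for Part II only"). Item 6 is a general clause: "Other medical conditions, in the judgment of the clinician investigator, that would increase the risks to the child" through taking part. Sections 15.1 and 15.2 allow study treatment to be stopped, or the child withdrawn, when continuing is judged not to be in the child's interest.

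Section 13.1, step 6, calls for a medical history and a check against the criteria. The note closing that section allows steps 1 to 7 to fall before the MRI day.

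**The concern.** The protocol names two high-risk groups and writes a fixed rule for only one of them. The group without a rule has the higher quoted risk range. A child in acute renal failure whose eGFR is 40 or more meets the letter of item 4 and could be given Ablavar unless a clinician steps in.

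This matters mainly in Part I, where item 5 is switched off. Part I accepts a child who "or is transferred from the neonatal ICU already sedated and intubated". If the guardians leave the choice of agent to the clinician, section 11.1.1 says that "the patient will be assigned the group that is under-enrolled with reference to the target enrollment", and that group may be Ablavar.

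What is at stake is an avoidable exposure in a setting the protocol has already identified as hazardous. No efficacy result is in question.

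**Working it through.** No figure in the plan needs to be reproduced. The check sets the risk statement beside the rules, then bounds the size.

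1. **Are the two risk groups distinct?** Section 4.4 lists them separately with different ranges: 1-7% for eGFR below 30 and 12-20% for acute renal failure. The ranges do not overlap, since 12 is above 7. An eGFR cutoff does not by definition cover the second group.

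2. **Does any exclusion name acute renal failure?** Taking section 9.3 in order:
   - Item 1: contraindications to MRI. No.
   - Items 2 and 3: iron overload and iron hypersensitivity. No.
   - Item 4: eGFR below 40 only. It catches acute renal failure when eGFR is below 40, and not otherwise.
   - Item 5: critical illness, Part II only. It is framed around anesthesia and separation from intensive care. If Part II used Ablavar it might remove some such children, again by judgment.
   - Item 6: any condition the investigator judges to raise risk. It can apply, but it is discretionary and has no renal wording.

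3. **Is there a bar elsewhere?** The discussions with referring clinicians and guardians (section 7.2; section 13.1, steps 1 and 2) come before dosing but set no rule. Sections 15.1 and 15.2 can be used, also at discretion. Section 9.1 says eGFR below 40 is not expected and is silent on acute renal failure.

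4. **Is there room above the cutoff?** Section 4.4 gives a GFR of 66 mL/min/1.73m² two weeks after birth. A fall to exactly 40 is 66 - 40 = 26, and 26 / 66 = 39%. The child would still not meet the below-40 rule. The protocol does not define acute renal failure, so whether a 39% fall would count is an assumption. This is an illustration and not an estimate of how often it happens.

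5. **How many could be exposed?** Part I plans 40 Ablavar children (section 7.2). If Part II also used Ablavar, the total is 40 + 40 = 80. The documents give no frequency of acute renal failure in this population, so no case count is offered.

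6. **How large is the absolute risk?** Section 4.4 reports 10 biopsy-proven pediatric NSF cases in all, none new in children since guidelines were introduced, and none in very young children. The Ablavar dose is 0.03 mmol/kg (section 12.2.2.2) against the cited limit of 0.1 mmol/kg: 0.03 / 0.1 = 30%.

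**The case against.** The strongest reply is that the plan is already cautious. Item 4 is set at 40, which is 10 above the line of 30 where section 4.4 places the highest eGFR-based risk. A child in acute renal failure with a current eGFR below 40 is therefore excluded. Item 6 fits the remaining case well, because the protocol itself describes acute renal failure as raising risk, and section 15.1 lets clinicians stop at any time. The advice on delay is background from one review, so section 9.3 contradicts no protocol rule. All of this stands, and it limits the weight of the point. It does not turn a discretionary safeguard into a stated one.

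Several stronger readings are tempting, but the documents do not support them:

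- *The plan lets an outdated eGFR clear a child.* A reader might infer this because sections 12.1 and 13.1 schedule no renal test and screening may precede the MRI day. Silence is not permission. Item 4 speaks of the subject's renal status, and step 6 requires it to be checked.
- *The 12-20% risk applies to these children.* It is a general figure for acute renal failure, with nothing to tie it to young children with eGFR of 40 or more at this dose.
- *Sick children are being steered to Ablavar.* Section 9.1 says that "the PDB is greatest in the smallest and sickest children", where PDB means prospect of direct benefit. Sections 4.5 and 5 use that term for Feraheme-enhanced MRI, so the remark explains the age range. The rule for deferring guardians does not override the exclusions.
- *Exclusion 6 is the only remaining safeguard.* Sections 15.1 and 15.2 also apply.

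**Conclusion.** The point holds as a minor safety gap in a stated rule. Section 4.4 separates acute renal failure from low eGFR and puts it at higher risk. Exclusion 4 does not mention it. In Part I, only discretionary provisions would keep Ablavar from a child in acute renal failure with an eGFR of 40 or more.

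The expected effect is very few children at very low absolute risk, with no effect on the primary endpoint, power or analysis. This rests on two assumptions: that acute renal failure can coexist with an eGFR of 40 or more in this population, which section 4.4's separate listing suggests but does not quantify; and that such children are uncommon, which the documents neither state nor contradict. The change is worth making because it costs almost nothing.

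**What to change.** Reword item 4 of section 9.3, and the matching synopsis item, to exclude from Ablavar *subjects with acute renal failure (acute kidney injury) at the time of MRI, regardless of eGFR, or with eGFR < 40 mL/min/1.73m²*. The investigators should state which definition of acute renal failure they use.

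In section 13.1, add a confirmation on the MRI day, before Ablavar is given, based on current clinical status and the renal function value already available, with the date of that value recorded.

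No new mandatory blood test is proposed. The cost is one clause in two places, one dated entry, and possibly a few lost Ablavar enrolments. As under the present item 4, an affected child who is otherwise eligible could still join the Feraheme group in Part I. Sample size and analysis stay as they are.
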